8.13. Measurement of energy intake by energy balance method

Energy intake will be calculated from total daily energy expenditure measured by DLW and the changes in body energy stores (Δ ES) using the following equations: Energy intake (kcal/d) = Total daily energy expenditure + Δ Energy Stores where, Δ energy stores, was calculated using the actual change in fat mass (kg) and total fat-free mass (kg) between the late pregnancy (weeks 35 to 37) and early pregnancy testing (weeks 13 to 16) multiplied by the energy coefficients for fat mass and total fat-free mass. The energy density of fat mass has been well-established as approximately 9300 kcal/kg and has been validated in pregnant women [68]. Energy density of fat-free mass differs during pregnancy [69] and we will use 771 kcal/kg as previously determined for pregnant women [70]. Therefore: Δ Energy stores (kcal/d) = (9300 x Δ fat mass, kg/d) + (771 x Δ total fat-free mass, g/d).

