8.12. Measurement of maternal body composition

MRI will be used to quantify total adipose tissue mass, skeletal muscle mass and non-adipose tissue mass volumes in the mother during pregnancy and at 12 months postpartum. To investigate the contribution of the fetus to energy metabolism, we will estimate maternal fat mass and fat-free mass both with and without the inclusion of fetal size.

Total adipose tissue volumes (called fat mass, FM) will be measured by MRI and converted to kilograms as previously described [65-67]. Non-adipose tissue volume (called fat-free mass, FFM) will be calculated as;

$$FFM_{TOTAL} \text{ (kg)} = \text{Total maternal mass including fetus (kg)} - \text{fat mass (kg)}$$

$$FFM_{Maternal} \text{ (kg)} = [\text{maternal mass} - \text{fetal size* (kg)}] - \text{fat mass (kg)}$$

*The mass of the fetus will be measured with 3-D ultrasound as described above.

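### The energy-stores formula in section 8.13 multiplies a kcal/kg coefficient by fat-free mass in g/d; taken literally, that one term is 1000 times too large

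*Combined protocol and SAP*

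**What the plan says.** Section 8.13 obtains energy intake by adding the daily change in body energy stores to total daily energy expenditure from doubly labeled water. It describes the change in stores twice.

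- **In words.** The change "was calculated using the actual change in fat mass (kg) and total fat-free mass (kg) between the late pregnancy (weeks 35 to 37") and the early visit is multiplied by an energy coefficient for each tissue. The fat mass coefficient is about 9300 kcal/kg. For fat-free mass, "we will use 771 kcal/kg as previously determined for pregnant women".
- **As an equation.** The first part reads "Δ Energy stores (kcal/d) = (9300 x Δ fat mass, kg/d"), and the second part is "771 x Δ total fat-free mass, g/d".

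Section 8.12 derives total fat-free mass in kilograms, as total mass including the fetus minus fat mass. Neither section gives a coefficient in kcal/g or a conversion factor. Section 3.1 lists intake by the energy balance method as a primary outcome. Section 10.2 analyses it for Aim 1 without restating the calculation.

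**The concern.** A coefficient in kcal/kg multiplied by a rate in g/d does not give kcal/d. The first term of the equation is consistent and the second is not, so the two cannot be added as printed.

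This is the only place where the energy-stores calculation is set out as an equation in daily rates. Anyone programming or replicating the primary outcome will go to it. If the printed unit were followed, the fat-free mass term would swamp both expenditure and fat deposition, and calculated intake would become in effect a scaled measure of fat-free mass gain. The comparison of High Gainers with Normal Gainers under Hypothesis 1, and the Bland-Altman comparison with the mathematical model, would then lose their meaning.

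**Working it through.** The plan gives no worked value of the energy-stores term, so there is no stated figure to reproduce. The check is one of units, followed by an example.

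**Inputs**

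- Fat-free mass coefficient: 771 kcal/kg (section 8.13).
- Fat mass coefficient: 9300 kcal/kg (section 8.13).
- Testing windows: weeks 13-16 and weeks 35-37 (section 8.13). Shortest interval: (35 − 16) × 7 = 133 days. Longest: (37 − 13) × 7 = 168 days.
- Fat-free mass gain: not in the documents; assumed to be 5-8 kg.
- Scale of plausible intake: 2617 and 3503 kcal/d in the preliminary data (section 2.1); planning SD 700 kcal/d (section 10.1).

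**Units**

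- As printed: 771 × (1000 × gain in kg ÷ days).
- Consistent with the coefficient: 771 × (gain in kg ÷ days).
- The ratio is exactly 1000, whatever the gain or interval.

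**Size of the fat-free mass term**

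| Assumed gain | Interval | As printed (kcal/d) | With kg/d (kcal/d) |
|---|---|---|---|
| 5 kg | 168 d | 22,946 | 22.9 |
| 5 kg | 133 d | 28,985 | 29.0 |
| 8 kg | 168 d | 36,714 | 36.7 |
| 8 kg | 133 d | 46,376 | 46.4 |

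The extremes come from the smallest gain over the longest interval and the largest gain over the shortest.

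**Without the 5-8 kg assumption**

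- Each kg of fat-free mass gained contributes 771 ÷ 168 = 4.6 to 771 ÷ 133 = 5.8 kcal/d in consistent units. As printed, it contributes 4,589 to 5,797 kcal/d.
- As printed, the gain that adds one planning SD is 700 ÷ 771 = 0.908 g/d. That is 0.12 kg over 133 days or 0.15 kg over 168 days.

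**The other term.** Each kg of fat contributes 9300 ÷ 168 = 55 to 9300 ÷ 133 = 70 kcal/d. This term is correct as printed.

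**The case against.** The strongest reply is that the paragraph settles its own meaning. The sentence before the equation puts both mass changes in kg, the coefficient is given per kg, the result is in kcal/d, and section 8.12 produces fat-free mass in kg. Going wrong would require an analyst to convert to grams while keeping a per-kg coefficient. The resulting intakes, in the tens of thousands of kcal/d, would be noticed at once. In correct units the term is small: 23-46 kcal/d is about 3-7% of the 700 kcal/d SD.

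All of this stands, and it limits the weight of the point. It does not remove the contradiction from the written formula for a primary outcome.

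A reader might infer three stronger things that the documents do not support:

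- **That calculated intake is 1000 times too large.** Only the fat-free mass term is affected; expenditure and the fat mass term are not.
- **That the preliminary intakes or the sample size carry the error.** Intakes of 2617 and 3503 kcal/d could not arise from the literal formula with even 1 kg of fat-free mass gain, since that term alone would exceed 4,500 kcal/d. Table 4 rests on an SD of 700 kcal/d taken from earlier data, not on this line.
- **That the trial's analysis will be wrong.** Nothing in the documents shows that the code follows the printed unit.

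**Conclusion.** The point holds as an internal contradiction in section 8.13. The fat-free mass unit in the equation disagrees with its coefficient, with the preceding prose, with the fat mass term and with section 8.12. Read literally, it inflates that one term by a factor of exactly 1000. The factor needs no assumption. The range of about 22,900-46,400 against 23-46 kcal/d rests on the assumed gain of 5-8 kg and on the interval from the testing windows.

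The intended unit is clear, so this is most likely a slip, and one that would show itself in the output. It is worth correcting because the formula defines a primary outcome, and a repair made silently during analysis would be an undocumented departure from the written plan.

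**What to change.** In section 8.13, change the fat-free mass unit so that the equation reads: ΔES (kcal/d) = 9300 × ΔFM (kg/d) + 771 × ΔFFM_total (kg/d). Confirm that the analysis code uses kg/d for both terms. A hand calculation for one participant is enough: each kg of fat-free mass gained should add about 4.6-5.8 kcal/d over 168-133 days.

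The cost is one unit in one formula and a brief check of the code. No design feature, sample size or other analysis changes.

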8.14. Changes in energy expenditure during pregnancy

We will measure each component of energy expenditure. Sleeping metabolic rate and resting metabolic rate will be measured directly in the metabolic chamber as described above. Total daily energy expenditure will be

measured directly by doubly labeled water as described above. Each component of energy expenditure will be studied according to following steps:

- Absolute change in energy expenditure (unadjusted). The absolute change in energy expenditure will be derived by taking the differences between two measurements of energy expenditure:
- Unadjusted = Late pregnancy energy expenditure (kcal/d) – Early pregnancy energy expenditure (kcal/d)
Change in energy expenditure (adjusted). To adjust energy expenditure measures for changes in maternal and fetal mass, linear regression equations will be created for each measure of energy expenditure with fat mass, fat-free mass (FFM_{TOTAL}) and maternal age as independent variables (data from baseline will be used). We will use the actual measurement of fat mass, fat-free mass and maternal age late pregnancy to predict energy expenditure at this time point. The difference between actual and predicted energy expenditure will be calculated and defined as Adjusted. We will also run these models with maternal fat-free mass (FFM_{Maternal}) and fetal mass independently.

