3.1. Primary outcomes

The primary outcome variables are 1) energy intake during pregnancy and 12 months postpartum measured with the energy balance method and with a mathematical model of maternal energy intake, and 2) the free-living energy expenditure and sleeping metabolic rate (absolute and adjusted for maternal body composition and fetal size) during pregnancy.

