10.2. Data analysis plan

Analyses will be performed in SAS version 9.3 (SAS Institute, Cary, NC). Statistical significance will be set at $p \leq 0.05$.

Aim 1: Mixed models will be used to analyze differences between 'High Gainers' and 'Normal Gainers' with respect to energy intake during pregnancy estimated with the energy balance method. Adjustments for covariates, such as maternal age, fetal size and parity will be made if appropriate. Least square means will be compared with the mixed models contrasts. Energy intake from the energy balance model will be analyzed analogously in the context of repeated measurements. We expect that energy intake by the two methods will all be significantly higher in 'High Gainers' versus 'Normal Gainers'. In addition, the two methods for measuring energy intake will be cross validated with each other and compared with Bland-Altman analysis. Regression analyses will be used to assess the relationship between energy intake during pregnancy and postpartum weight loss after 1 year. We predict that lower energy intake during pregnancy is associated with better postpartum weight loss results after 1 year.

Aim 2: Analysis of covariance will be used to assess significance of differential changes ('High Gainers' versus 'Normal Gainers') in absolute energy expenditure. Differential changes in energy expenditure after adjustment for changes in maternal and fetal size will be tested analogously. For secondary hypotheses, change in energy expenditure attributable to accelerometer-measured physical activity (steps per min) will be analyzed to investigate its role in differential energy balance in 'High Gainers' versus 'Normal Gainers'.

Analyses of exploratory aims: The change in determinants of energy intake and energy expenditure in blood and urine from early to late pregnancy and 12 months postpartum will be analyzed by repeated measures with IOM classification and time interactions. Adjustments for covariates, such as maternal age, fetal size, parity and early pregnancy values will be made if appropriate. To control for type I error, statistical significance for all multiple comparisons will be adjusted using the Tukey-Kramer method.

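### The adjusted change in energy expenditure is a late-pregnancy residual: the early residual is never removed, so an early group difference can pass as a differential change

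*Combined protocol and SAP*

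**What the plan says.** Section 8.14 defines two measures for each component of energy expenditure.

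- The first takes each woman's early value away from her late value: "Unadjusted = Late pregnancy energy expenditure (kcal/d) – Early pregnancy energy expenditure (kcal/d".
- The second is also introduced as a change: "Change in energy expenditure (adjusted). To adjust energy expenditure measures for changes in maternal and fetal mass, linear regression equations will be created". The predictors are fat mass, total fat-free mass and age, and the equation is fitted at the early visit: "maternal age as independent variables (data from baseline will be used". It is then applied at the late visit only: "We will use the actual measurement of fat mass, fat-free mass and maternal age late pregnancy to predict energy expenditure at this time point". The section ends with "The difference between actual and predicted energy expenditure will be calculated and defined as Adjusted".

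Section 3.1 lists as a primary outcome "the free-living energy expenditure and sleeping metabolic rate (absolute and adjusted for maternal body composition and fetal size) during pregnancy". For Aim 2, section 10.2 compares changes in absolute expenditure between High and Normal Gainers by analysis of covariance, and then says "Differential changes in energy expenditure after adjustment for changes in maternal and fetal size will be tested analogously". It names no covariates for Aim 2. Early-pregnancy values are mentioned as possible covariates only for the exploratory blood and urine analyses. Section 8.11 forms the groups from gestational weight gain at delivery.

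**The concern.** The label and the test say change, but the formula gives a level at one visit. Early data enter only through the fitted coefficients. A woman who sits 100 kcal/d above the equation at both visits scores +100 on the adjusted change, although her change is 100 − 100 = 0.

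In a randomised comparison such standing differences would balance on average. Here the groups are defined by weight gain, so nothing makes them alike in early-pregnancy expenditure for a given body size. The study asks whether a failure of expenditure to rise contributes to excess gain. A standing difference and a differential change answer that question differently, and the planned measure cannot separate them. An offset could produce an apparent differential change, or cancel a real one.

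**Working it through.** **1. The plan's nearest figure.** The documents give no SD, power or sample size for adjusted expenditure. The nearest is Table 4 for energy intake: SD 700, difference 590 kcal/d, 17 and 34 women, power 0.80. (The text of 10.1 attaches a different power to 590; that is a separate matter.)

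- SE = 700 × √(1/17 + 1/34) = 700 × 0.297 = 207.9
- 590/207.9 − 1.96 = 0.88, so power is 0.81 by the normal approximation and 0.79 by the noncentral t.

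The row reproduces, and I use its group sizes below.

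**2. What the formula contains.** For one woman:

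- Adjusted (8.14) = late actual − late predicted
- Change beyond that expected from body size = (late actual − early actual) − (late predicted − early predicted)
- The first minus the second = early actual − early predicted, the early residual.

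So the group difference in Adjusted equals the group difference in adjusted change plus the group difference in early residual.

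**3. Size of the carry-over.** The section 8.14 procedure was simulated with 3,000 runs per setting and two-sided tests at 0.05.

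Inputs from the documents: group sizes, alpha, and the equation in fat mass, fat-free mass and age.

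Assumptions:
- residual SD 200 kcal/d at both visits, with early–late residual correlation ρ of 0.3, 0.5, 0.7 or 0.85;
- early means (SD) of 42 (8) kg fat mass, 55 (6) kg fat-free mass and 28 (5) years;
- mean gains of 1 kg fat and 6 kg fat-free mass, with 3 kg and 1.5 kg more in High Gainers;
- no true differential change;
- an early offset between groups of 0, 100 or 200 kcal/d.

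| Early offset | Adjusted as written: difference; significant | Late minus early residual: difference; significant |
|---|---|---|
| 0 | about 0; about 5% | about 0; 5–7% |
| 100 | about 94; 33–36% | about 0; 4–7% |
| 200 | about 187; 85–88% | about 0; 5–7% |

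Carry-over is 94% rather than 100% because three predictors fitted to 51 women absorb by chance about 3/50 = 6% of a group contrast.

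Check: the SE is 200 × 0.297 = 59.4, simulated as about 60. Then 94/60 − 1.96 = −0.39, a probability of 0.35; and 187/60 − 1.96 = 1.16, a probability of 0.88. By the same arithmetic an offset of 50 kcal/d would appear as 47 kcal/d: 47/60 − 1.96 = −1.18, or about 12% significant.

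**4. Precision.** With equal SDs at the two visits, variance relative to the late residual is 2(1 − ρ) for subtraction and 1 − ρ² for analysis of covariance on the early residual. The smallest difference detectable with 80% power is (1.96 + 0.84) × 0.297 = 0.83 residual SDs for the late residual. It is multiplied by the square root of those ratios for the other two.

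| ρ | Late residual | Subtraction | Covariance |
|---|---|---|---|
| 0.3 | 0.83 | 0.99 | 0.79 |
| 0.5 | 0.83 | 0.83 | 0.72 |
| 0.7 | 0.83 | 0.65 | 0.59 |
| 0.8 | 0.83 | 0.53 | 0.50 |

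Simulated SEs with no offset, late residual versus subtraction, were 60 versus 72 kcal/d (ρ = 0.3), 60 versus 60 (0.5), 60 versus 48 (0.7) and 59 versus 35 (0.85).

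**5. Covariance adjustment instead of subtraction.** With an early offset of 100 kcal/d, analysis of covariance on the early residual leaves 65, 46, 29 and 15 kcal/d at ρ = 0.3, 0.5, 0.7 and 0.85. It is significant in 19% down to 9% of runs.

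**The case against.** The strongest reply is that Hypothesis 2 (section 2.2) and the primary outcome (section 3.1) speak of adjusted expenditure, not of change in it. For a question about level, a late residual from a common equation is a legitimate measure, and a standing group difference is signal. This stands as a reading, but sections 8.14 and 10.2 both call the quantity a change. The sections conflict, and the estimand for part of a primary outcome is unsettled.

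Secondly, an analysis of covariance needs a covariate, and the early value is an obvious candidate. It is not excluded, but it is not named for Aim 2 either, and step 5 shows that it would remove only part of an offset.

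Thirdly, residuals from an equation fitted at the early visit average zero over the fitted sample. The overall mean of Adjusted therefore does reflect change. That is correct; only the between-group comparison is exposed, but it is the one being tested.

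A reader might also infer that the planned measure necessarily loses precision. The documents do not support that. Against subtraction it holds only if ρ exceeds 0.5; they give no ρ, and the visits are about 20 weeks apart. Nor are subtraction and covariance adjustment interchangeable, since they diverge when groups differ at the start.

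**Conclusion.** The point holds as a mismatch between name, test and formula. What is called an adjusted change is a late residual, and about 94% of any early-pregnancy group offset enters the comparison in the simulated setting. The identity in step 2 needs no assumption. The rejection rates rest on an assumed residual SD of 200 kcal/d and assumed offsets.

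A reader might go further and conclude that the Aim 2 result will be biased, or that pre-pregnancy differences are the source. Nothing in the documents shows that an offset exists, and the earliest expenditure measurement is at weeks 13–16, so only early-pregnancy differences can be discussed. If Hypothesis 2 is meant as a level, the formula can stay and the labels must change. I rate this should-fix.

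**What to change.** - In 8.14, define adjusted change = (late actual − late predicted) − (early actual − early predicted), both from the same early-pregnancy equation, for total daily expenditure, sleeping metabolic rate and resting metabolic rate. Treat the alternative models, with maternal fat-free mass and fetal mass entered separately, the same way.
- In 10.2, use this quantity for the differential-change test and name the Aim 2 covariates.
- Report the late residual separately as an adjusted level, and state whether Hypothesis 2 concerns level or change.
- Add an analysis of covariance of the late residual on the early residual as a sensitivity analysis. It gains precision at any nonzero correlation but leaves part of a baseline offset, so it supplements subtraction and does not replace it.

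The cost is a few sentences. Table 1 already schedules doubly labelled water, chamber and MRI measurements at both the early and late visits, so no new data are needed. Two downsides should be accepted openly: subtraction widens the interval if ρ is below 0.5 (SE 72 versus 60 kcal/d at 0.3), and a woman without complete early data has no adjusted change. Settling this before analysis avoids choosing between two estimands after seeing the results.

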8.15. Measurement of changes in physical activity during pregnancy

Physical activity will be estimated from total daily energy expenditure by doubly labeled water and resting metabolic rate using two different calculations. First the physical activity level (PAL) will be calculated by the widely accepted method of dividing total daily energy expenditure (TDEE) by sleeping metabolic rate (RMR) as; $PAL = TDEE/RMR$. Because of the inherent problem of using ratios when the two variables have an intercept not equal to zero [71], we will also express physical activity as the residual value of the regression between measured TDEE and measured RMR [72]. This value, termed Activity Related Energy Expenditure (AREE), is positive for subjects with higher physical activity than average and negative for subjects with lower physical activity than average independent of metabolic body size. Because AREE is adjusted for metabolic body size (RMR), this value is directly proportional to the amount of physical activity. We have previously used both approaches to study changes in physical activity during calorie restriction [73].

8.16. Placenta biospecimens

For participants who provide permission, as soon as possible (preferably within 60 minutes of delivery), the delivered placenta will be weighed, photographed and the following biospecimens will be collected:

- **Basal plate tissue:** samples of the basal plate (the maternal side) will be collected and stored at PBRC.
- **Villous tissue:** samples of the villous tissue (inner placental layer) will be collected and stored at PBRC.
- **Chorionic plate tissue:** samples of the chorionic plate (the fetal side) will be collected and stored at PBRC.
- **Cord Blood:** Attempted collection will be completed with as much blood as possible that can be extracted from the placenta (average extraction is 50 mL). **Note:** as cord blood supply is only to the fetus and not the mother, an attempted maximum collection implies no increased risk to baby (as s/he is already separated from the cord) or the mother.
- **Umbilical cord tissue:** small (approximately than 1 inch in length) sections of the umbilical cord will be collected and stored at PBRC.
- **Fetal membranes:** a small section of membrane (approximately 10 cm x 10 cm) will be collected and stored at PBRC.

In the case where a request for placental examination is made by the physician, study staff will attempt to coordinate with pathologists to obtain samples in order to preserve the tissue for histological analysis. Placental biospecimens will be snap frozen in liquid nitrogen, preserved for immunohistochemistry or the fresh tissue will be prepared for isolation of trophoblast cells.

The specimens collected at delivery will be collected at community hospitals where the hospital has approved this procedure, as defined by the community hospital policies and procedures. If the PI does not have permission from the hospital or it is not possible to collect the specimen for any other reason, regardless of the subject's consent to the procedure, the specimen collection procedure will not be done.

